3.1.5. Group C Phase 1b (Dose Escalation): Entospletinib Monotherapy

Note: At the time of this amendment, Group C Phase 1b had completed enrollment.

ENTO monotherapy will be administered orally every 12 hours at the dose level indicated in the table below for every 28-day cycle until the subject meets criteria for study treatment discontinuation. The initial dosing level for the 1st cohort is defined as level 0 in table below.

Intra-subject dose escalation will not be allowed.

Table 3-5. Group C Entospletinib Cohort Dose Escalation Table

Dose Level	Entospletinib
0	400 mg
1	800 mg

Subjects will receive ENTO continuously on Days 1-28 of a 28-day cycle until the subject meets criteria for study treatment discontinuation (see Section 6.4.1). A bone marrow biopsy and aspirate sample will be collected for disease assessment and biomarker research on Cycle 1 Day 28 and Cycle 2 Day 28.

A bone marrow aspirate sample will be collected for disease assessment and biomarker research every 4 cycles starting on Cycle 4 Day 28 of subsequent cycles (ie, Cycle 4 Day 28, Cycle 8 Day 28) unless the subject achieved CR/CRi, in which case further marrow aspirations are not required, unless clinically indicated (exception: if the subject clearly has circulating leukemia cells in the peripheral blood, bone marrow aspiration after Cycle 2 or beyond is not mandated).

If a subject discontinues study treatment (eg, as a result of an AE), every attempt should be made to keep the subject in the study to perform the required study-related follow-up and procedures. If this is not possible or acceptable to the subject or investigator, the subject may be withdrawn from the study.

3.1.6. Group C Phase 2 (Dose Expansion): Entospletinib Monotherapy

Note: At the time of this amendment, Cohort C1A had completed enrollment (n=15). This amendment identifies the closure of Cohort C3 to further enrollment (n=12).

Relapsed/refractory and previously untreated subjects will be evaluated in separate cohorts during phase 2 as monotherapy. ENTO 400 mg will be administered orally every 12 hours on Days 1-28 of every 28-day cycle as long as the subject is experiencing benefit and does not meet criteria for study treatment discontinuation.

A bone marrow biopsy and aspirate sample will be collected for disease assessment and biomarker research at the end of Cycles 1 and 2 on Day 28. A bone marrow aspirate sample will also be collected for disease assessment and biomarker research on Day 28 of every 4 cycles beginning on Cycle 4 Day 28 (eg, Cycle 4 Day 28, Cycle 8 Day 28) and at suspected disease progression. Subjects who achieve CR/CRi that is stable for 2 consecutive bone marrow evaluations are not required to have further bone marrow aspirate samples collected, unless clinically indicated.

Cohort C1A: This cohort is designed to enroll 15 relapsed/refractory AML subjects. If 5 or more of the initial 15 subjects achieve CR/CRi after 1-2 cycles, an additional 15 subjects would then be enrolled. However, if less than 5 of the initial 15 subjects achieve CR/CRi after 1-2 cycles, then treatment would be considered futile. At this time, futility has been met and, thus, Cohort C1A will not move forward (ie, will not enroll any subjects).

Cohort C2: 15 relapsed/refractory AML subjects with MLL.

Cohort C3: 30 previously untreated AML subjects who are unfit (eg, very elderly, have multiple comorbidities, and a poor ECOG/performance status) for chemotherapy or hypomethylating agent, or refuse either of these 2 treatment options.

If a subject discontinues study treatment (eg, as a result of an AE), every attempt should be made to keep the subject in the study to perform the required study-related follow-up and procedures. If this is not possible or acceptable to the subject or investigator, the subject may be withdrawn from the study.

3.2. Dose Limiting Toxicities

It is recognized that drug-related toxicity in this population may be difficult to ascertain given the aggressive hematologic disease. Investigators will attempt to assign attribution of toxicities to each drug when possible. The CTEP Active Version of the NCI Common Terminology Criteria for Adverse Events (CTCAE) version 4.03 will be utilized for AE reporting.

The assessment of DLTs for dose escalation decisions will occur during the DLT assessment window. DLTs will also be assessed in Phase 2 during the Group B safety run-in to evaluate the safety of ENTO in combination with azacitidine. The DLT assessment window for each group is as follows:

Group A: begins on Cycle 0 Day 1 and ends 28 days after Cycle 1 Day 1 or 28 days after Cycle 2 Day 1 (if Cycle 2 is needed); for subjects with < 5% blasts in the bone marrow, the DLT window may be expanded for hematologic toxicity recovery as noted below

Group B (including Phase 2 safety run-in): begins on Cycle 0 Day 1 and ends 28 days after Cycle 1 Day 1

Group C: 28 days (Cycle 1); for subjects with < 5% blasts in the bone marrow, the DLT window may be expanded for hematologic toxicity recovery as noted below

During the DLT assessment window, subjects who fail to complete 21 days of ENTO, or miss any doses of cytarabine and daunorubicin in Group A, or decitabine (or azacitidine during the Phase 2 safety run-in) in Group B for reasons other than DLT, will not be evaluable for the ENTO DLT assessment. Additional subjects will be enrolled to the appropriate dose level to replace unevaluable DLT subjects in order to provide adequate safety data on which to base dose escalation decisions as well as expansion decisions. Non-hematologic toxicity of Grade 4 attributable to ENTO with the exception of alopecia, nausea and vomiting controllable with anti-emetic therapy, line associated venous thrombosis, infection (infection-related toxicities such as fever/sepsis), and fatigue will be considered DLT.

Subjects with transient Grade 4 electrolyte abnormalities that are not clinically significant and are correctable within 24 hours will not be considered DLT.

Subjects with transient liver function test abnormalities (AST, ALT, bilirubin, or alkaline phosphatase) that resolve to \leq Grade 2 within 10 days will not be considered DLT.

In general, infection will not constitute a DLT unless it is felt that the infection resulted from unexpectedly complicated prolonged myelosuppression.

Toxicities that require temporary interruption of treatment with ENTO (but not permanent discontinuation) will not be considered DLT unless the toxicity does not resolve to \leq Grade 2 in 10 days.

In subjects with < 5% blasts in the bone marrow, absence of myelodysplastic changes, and/or absence of AML by flow cytometry in the bone marrow, hematologic toxicity will be defined as: failure to recover neutrophil count ($ANC > 500/\mu L$) or platelet count ($> 25000/\mu L$) within 4 weeks after achieving < 5% blasts in Group A and Group C. Hematologic toxicities will not be used to assess DLTs in Group B.

3.2.1. Guidelines for Phase 1b Dose Escalation and Phase 2 Group B Dose Expansion

In Phase 1b, the trial employs the standard NCI definition of MTD (starting dose associated with DLT in <33.3% of subjects during the DLT assessment window). After considering the available safety and efficacy data and in consultation with the study PI, a dose at or below MTD will be chosen by the sponsor for further evaluation.

Dose escalation for Groups A, B, and C will proceed independently and in parallel per [Table 3-6](#).

Table 3-6. Dose Escalation/ DLT Guidelines

Number of Subjects with DLT at a given level	Escalation Decision Rule
0 out of 3	Enroll 3 subjects at the next dose level. An additional 3 subjects can be enrolled at the current dose level without a DLT if additional evaluation is warranted after discussion with the study PI and medical monitor.
≥ 2	Dose escalation will be stopped. This dose level will be declared maximally administered dose (highest dose administered). Three (3) additional Pts. will be entered at next lower dose level if only 3 subjects were treated previously at that dose.
1 out of 3	Enroll at least 3 more subjects at this dose level. If 0 of these 3 subjects experience DLT, proceed to the next dose level. If 1 or more of this group suffer DLT, then dose escalation is stopped, and this dose is declared the maximally administered dose. Three (3) additional subjects will be entered at the next lower dose level if only 3 subjects were treated previously at that dose.
≤ 1 out of 6 at highest dose level below the maximally administered dose	This is the maximum tolerated dose (MTD) and generally the effective dose. At least 6 subjects must be entered at the effective dose. The recommended expansion dose may be a dose lower than the MTD.

In Phase 2 Group B (ENTO + azacitidine) safety run-in cohort, if 2 or more subjects experience DLT, all ongoing subjects in the cohort will be discontinued and the cohort will be closed.

3.3. Dosing Delays/Dose Modifications Attributed to Entospletinib (Beyond Cycle 1)

If the following signs or symptoms are medically manageable, they are not to be a consideration with respect to the subject’s dosing or continuation on study: nausea/mild vomiting/diarrhea, drug-related fever or chills, transient and correctable laboratory test abnormalities, line associated thrombosis, or alopecia (see [Appendix 3](#)). Subjects who are intolerant of dose beyond Cycle 1, may either stop study drug (permanent discontinuation) or have a dose hold in consultation with the Medical Monitor if the AE or lab has resolved to Grade 1 or less which may not be re-escalated. If there is loss of disease control during drug interruption which has resolved to Grade 1 or less, subjects may re-start ENTO per the dose modification guidelines below.

Group A:

Subjects experiencing toxicity attributed to any of the study medication during Cycle 1 requiring permanent discontinuation of either drug shall be removed from study. There will be no dose modifications for ENTO for hematologic toxicity during Cycle 1.

Dose modification of ENTO in subsequent cycles is permitted following guidelines provided below. Subjects who experience a non-hematologic toxicity assessed as ENTO related that is Grade 3 or higher will hold dosing of ENTO until the toxicity resolves to Grade 1, and then restart at the next lower dose and continue through the end of the cycle. Missed doses are not to be made up.

Adverse events and laboratory abnormalities will be graded using the CTCAE, Version 4.03.

Dose Modifications for Non-Hematologic Toxicity for Entospletinib and Daunorubicin and Cytarabine and High Dose Cytarabine Maintenance

In subjects who experience flurid heart failure (EF < 45%) or cerebellar toxicity, protocol treatment will be held and no further anthracyclines or cytarabine will be permitted while on the trial. To re-administer and continue with protocol treatment, EF will need to recover to $\geq 45\%$.

If a subject experiences any non-hematologic clinically significant Grade 3 or greater toxicity felt to be related to the combination agents, or high dose cytarabine maintenance, hold the protocol therapy until it resolves to less than Grade 2. Then, if determined related to ENTO, restart ENTO with one dose level reduction. If a subject experiences pneumonitis at Grade 4, study treatment must be discontinued.

Dose Modifications for Hematologic Toxicity for Entospletinib and Daunorubicin and Cytarabine and High Dose Cytarabine Maintenance

No dose modifications are planned for hematological toxicity for cytarabine and daunorubicin during induction chemotherapy. In subjects who require Cycle 2 induction, an ECHO/MUGA is recommended prior to starting Cycle 2 and daunorubicin will be administered if EF is $\geq 45\%$ per investigator discretion.

No renal dose reductions are necessary when standard dose cytarabine is used (100-200mg/m²/24hrs). Reduced doses should be considered when using high dose cytarabine as indicated below:

Glomerular Filtration Rate (mL/min)	Dose Administered
> 60	100%
46-60	60%
31-45	50%
< 30	Contraindicated

For cerebellar neurotoxicity \geq Grade 2 due to high dose cytarabine, discontinue high dose cytarabine for the remainder of the induction cycle.

If prolonged hematologic clinically significant Grade 3 or greater toxicity felt to be related to ENTO occur after Cycle 1, hold ENTO until it resolves to less than Grade 2. Then, restart ENTO with one dose level reduction.

Group B:

Cycle 0 will be defined as Days 1-14. Cycles 1-4 and maintenance therapy will be defined as Days 1-28. Subsequent cycles of therapy are to begin as soon as possible after Day 28. Delays of up to 14 days will not constitute a protocol violation.

Delays of longer than 14 days must be discussed with the PI and Medical Monitor; repeat BM aspiration and biopsy is required if treatment is delayed more than 4 weeks. Delays longer than 14 days are only permitted (but not required) under special circumstances after discussion with PI and Medical Monitor and permissible reasons for these extended delays include:

- Drug related myelosuppression (defined here as ANC $<$ 500/ μ L or platelet count $<$ 25,000/ μ L, with no evidence of AML in blood or marrow – including flow cytometry or cytogenetics). A repeat BM aspiration and biopsy is required if treatment is delayed more than 4 weeks.
- Ongoing febrile neutropenia or active infection in subjects with no evidence of AML. Note - this does not apply to subjects with febrile neutropenia/infection in the setting of active AML.
- Serious hemorrhagic complication in a subject who is refractory to platelet transfusions.

For subjects entering the maintenance phase of treatment, drug related myelosuppression is a greater concern. However, it should again be noted that subjects with continued evidence of AML such as by flow or cytogenetics (even if morphologic blasts are $<$ 5%) should proceed with therapy in a timely way as described above.

For subjects with no evidence of AML, the first cycle of maintenance should proceed on Day 29 as long as marrow cellularity is \geq 10%. However, the second (or subsequent) cycles of maintenance therapy may be held until ANC is greater than or equal to 1000. If there is no evidence of ANC recovery after 14 days, repeat marrow evaluation is needed. If negative for disease and cellularity is \geq 10%, proceed with decitabine and ENTO at decreased doses. Bone marrow evaluation may be done sooner than 14 days at the discretion of the treating physician.

Dose Modifications for Non-Hematologic Toxicity for Entospletinib, Decitabine or Azacitidine

If the subject experiences any non-hematologic clinically significant Grade 3 or greater toxicity felt to be related to either agent during the induction phase beyond DLT assessment, hold the protocol therapy until it resolves to less than Grade 2. Then, if related to ENTO, restart ENTO

with one dose level reduction. If related to decitabine or azacitidine, the respective package insert should be followed for any dose reductions. If institutional guidelines are to be followed, contact the study team for additional guidance. If the toxicity recurs, subject will be removed from study. If protocol therapy is withheld for more than 2 weeks for toxicity related to protocol-based therapy or up to 4 weeks for any other reason, subjects will be removed from protocol. If a subject experiences pneumonitis at Grade 4, study treatment must be discontinued. For additional safety information, reference the package insert for decitabine and azacitidine.

Subjects who have been dose-reduced cannot be returned to a higher dose level.

Toxicities in an individual subject must resolve to less than Grade 2 or to baseline levels before proceeding with the next cycle of treatment.

Dose Modifications for Hematologic Toxicity for Entospletinib, Decitabine or Azacitidine

It is recognized that drug-related hematologic toxicity in this population may be difficult to ascertain given the aggressive hematologic disease and the fact that multiple cycles of therapy may need to be administered for maximal clinical response. Therefore, there will be no dose modifications for hematologic toxicity due to ENTO, decitabine or azacitidine during the first 3 cycles for subjects with active AML. However, after the third cycle of ENTO and decitabine is administered, subjects suspected to have study treatment related ANC and/or platelet count toxicity (ie, fail to recover to at least 50% of the prior cycle's baseline value) will have the dose of decitabine reduced to 20 mg/m²/d on Days 1-9 and the dose of ENTO reduced one dose level. Similarly, after the third cycle of ENTO and azacitidine administration, subjects suspected to have study treatment related ANC and/or platelet count toxicity (ie, fail to recover to at least 50% of the prior cycle's baseline value) will have the dose of azacitidine reduced according to [Table 3-7](#) and the dose of ENTO reduced one dose level. Dose modifications because of concern for drug induced cytopenias prior to Cycle 4 will be discussed with the medical monitor. Dose modifications for hematologic toxicity for subjects who have achieved a CR or CRi are detailed below. For additional safety information, reference the package insert for decitabine and azacitidine.

Table 3-7. Azacitidine Dose Modifications

Nadir Counts		% Dose in the Next Course
ANC (x10⁹/L)	Platelets (x10⁹/L)	
< 0.5	< 25.0	50%
0.5 –1.5	25.0-50.0	67%
> 1.5	> 50.0	100%

Dose Modifications for Hematologic Toxicity for Subjects Who HAVE Achieved < 5% Blasts and Receive Maintenance Therapy With Decitabine or Azacitidine

Subjects who have had a previous dose reduction of decitabine and ENTO and then subsequently have a decrease in blasts to < 5% by morphology, the number of days of decitabine will be reduced to Days 1-4 of each cycle, but the daily dose will remain the same. For example, a subject receiving 20 mg/m²/day on Days 1-9 will move on to receive 20 mg/m²/day on Days 1-4. Subjects will receive the same dose reduction of ENTO. For azacitidine, no dose reduction regimen is necessary.

Neutropenia

In the event of Grade 4 neutropenia (ANC < 500/μL) that occurs with the second or subsequent cycles of maintenance and persists for 14 days or more or is associated with febrile neutropenia, further cycles of ENTO/decitabine shall be administered once ANC recovers to ≥ 1000/μL with a decrease in the number of days of decitabine and the dose of ENTO will be decreased by 1 dose level (ie, for the first occurrence omit the final day 5 dose of decitabine; for the second occurrence omit the final day 4 dose of decitabine). If there is no evidence of ANC recovery after 14 days, repeat marrow evaluation should be considered. Subjects who require a dose reduction below dose level -1 will not receive ENTO and instead will continue maintenance treatment with decitabine alone. If Grade 4 neutropenia that persists for 14 days or more (or grade 4 neutropenia associated with fever) recurs for the third time, discontinue the ENTO/decitabine. Similarly, in the event of neutropenia that occurs with the second or subsequent cycles of maintenance with azacitidine, and persists for 14 days or more or is associated with febrile neutropenia, the dose of azacitidine will be reduced according to [Table 3-8](#).

Thrombocytopenia

In the event of Grade 4 thrombocytopenia (platelets < 25,000/μL) that occurs with the second or subsequent cycles of maintenance and persists for more than 14 days (or >25,000/μL but requiring prophylactic platelet transfusions to maintain this over the 14 day period), further cycles of ENTO/decitabine shall be administered with a decrease in the number of days of decitabine and the dose of ENTO will be decreased by 1 dose level (ie, for the first occurrence omit the final day 5 dose of decitabine; for the second occurrence omit the final day 4 dose of decitabine). Subjects who require a dose reduction below dose level -1 will not receive ENTO and instead will continue maintenance with decitabine alone. If Grade 4 thrombocytopenia persisting for more than 14 days (or subject requires prophylactic platelet transfusions to maintain >25,000/μL over the 14 day period) recurs for the third time, discontinue the ENTO/decitabine. Similarly, in the event of thrombocytopenia that occurs with the second or subsequent cycles of maintenance with azacitidine, and persists for 14 days or more or is associated with prophylactic platelet transfusions, the dose of azacitidine will be reduced according to [Table 3-8](#).

Table 3-8. Azacitidine Dose Reductions

WBC or Platelet Nadir % decrease in counts from baseline	Bone Marrow Biopsy Cellularity at Time of Nadir (%)		
	30-60	15-30	<15
	% Dose in the Next Course		
50 - 75	100	50	33
>75	75	50	33

Dose Modifications for Non-hematologic Toxicity for Subjects Who HAVE Achieved CR or CRi and Receive Maintenance Therapy With Decitabine or Azacitidine

Subjects who experience any significant Grade 3 or greater toxicity attributed to decitabine, azacitidine, or ENTO will hold the protocol therapy until it resolves to \leq Grade 2. Then restart ENTO with one dose level reduction and reduce the dose of decitabine to 20 mg/m²/d on Days 1-4 for the first occurrence and decrease the dose of decitabine to 20 mg/m²/d on Days 1-3 for the second occurrence and restart ENTO at the next lower dose. For azacitidine specifically, 50% dose reduction will be applied in combination with ENTO at the next lower dose. Subjects who require a dose reduction below dose level -1 will not receive ENTO and instead will continue maintenance with decitabine or azacitidine alone. If the toxicity recurs for a third time during treatment period, therapy should be discontinued. Decitabine/ENTO or azacitidine/ENTO should not be restarted until the toxicity has resolved to Grade 2 or better. Subjects with controlled Grade 3 infection or febrile neutropenia may continue decitabine or azacitidine in combination with ENTO. If a subject experiences pneumonitis at Grade 4, study treatment must be discontinued but may continue with decitabine or azacitidine alone.

Dose reductions (for either hematologic or non-hematologic toxicity) for subjects with < 5% blasts by morphology may be done twice during the course of maintenance therapy, if necessary.

Group C:

Dose modifications and delays attributed to ENTO for hematologic and non-hematologic toxicities will follow the guidelines in [Appendix 3](#).

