2. OBJECTIVES AND ENDPOINTS

2.1. Objectives

The primary objectives are:

- To demonstrate the overall safety of ENTO in combination with standard dose cytarabine and daunorubicin chemotherapy (7+3) in subjects with previously untreated AML who are candidates for chemotherapy (fit subjects) and to assess the efficacy of ENTO at the recommended Phase 2 dose (RP2D) (Group A)
- To demonstrate the overall safety of ENTO in combination with hypomethylating agents (decitabine or azacitidine) in subjects with previously untreated AML who are not candidates for 7+3 (unfit subjects) and to assess the efficacy of ENTO at the RP2D (Group B)
- To demonstrate the overall safety of ENTO monotherapy in subjects with previously untreated AML who are not candidates for chemotherapy or in subjects with relapsed/refractory AML with or without mixed-lineage leukemia (MLL) and to assess the efficacy of ENTO at the RP2D (Group C)

The secondary objectives of this study are:

- To assess the qualitative and quantitative toxicities of ENTO monotherapy or ENTO in combination with chemotherapy in subjects with AML
- To document therapeutic response of subjects with AML treated with ENTO monotherapy or ENTO in combination with chemotherapy

The exploratory objective of this study is:

- CCI [REDACTED]

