5. TREATMENT PLAN

5.1. Treatment Plan

5.1.1. Premedication

No specific premedications or supporting medications are required in conjunction with ENTO administration.

For cytarabine, daunorubicin, decitabine, and azacitidine please follow the currently approved version of the package insert and institutional guidelines when administering.

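### In Protocol Section 3.3 (Group A), one cerebellar-toxicity sentence names a period without high dose cytarabine, and restart after a cerebellar hold is tested only by ejection fraction

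*Protocol*

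**What the plan says.** Protocol Section 3.3 deals with cerebellar toxicity in Group A twice.

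The first rule is in the non-hematologic block. It joins two events, florid heart failure (EF below 45%) and cerebellar toxicity. In either case, the text reads "cerebellar toxicity, protocol treatment will be held and no further anthracyclines or cytarabine will be permitted while on the trial". No grade and no causal drug is given for the cerebellar event. The next sentence sets the restart condition for both events: "To re-administer and continue with protocol treatment, EF will need to recover to" 45% or more.

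The second rule is in the hematologic block, just after the renal dosing table for high dose cytarabine. For cerebellar neurotoxicity at or above "Grade 2 due to high dose cytarabine, discontinue high dose cytarabine for the remainder of the induction cycle".

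Between the two is a general rule. For clinically significant non-hematologic toxicity of Grade 3 or greater, related to the combination agents or to high dose cytarabine, sites must "hold the protocol therapy until it resolves to less than Grade 2".

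**The concern.** A dose-modification rule should name a period in which the drug is actually given, and a restart test should measure the toxicity that caused the hold. The second cerebellar sentence fails on the first count and the EF condition fails on the second.

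What is at stake is subject safety and uniform conduct across sites. A site that looks only at the block with the renal dosing table finds a sentence that is milder than the first rule and is written for the wrong treatment phase. A site that reads the restart sentence literally could resume ENTO in a subject whose cerebellar signs have not improved, because EF was never the problem.

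**Working it through.** No arithmetic applies. The check sets the texts side by side.

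**1. Where high dose cytarabine is given.** Section 2.1 describes Group A chemotherapy as standard dose 7+3, and Table 3-1 gives cytarabine at 100 mg/m². Section 3.1.2 gives Phase 2 induction as cytarabine on Days 1-7 with daunorubicin on Days 1-3, for up to 2 cycles. Gram doses (3 g/m² every 12 hours on Days 1, 3 and 5 below age 60; 1 g/m² daily on Days 1-5 from age 60) appear only in the post-remission cycles (Sections 3.1.2, 3.4 and 6.3.1). Sections 3.1.2 and 3.4 attach the high dose label to different regimens of this pair, but both are post-remission. Section 3.1.1 describes no post-remission phase for Phase 1b.

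**2. The two rules.**

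| | Non-hematologic block | Hematologic block |
|---|---|---|
| Trigger | Cerebellar toxicity, ungraded, any cause | Grade 2 or higher, due to high dose cytarabine |
| Drugs stopped | Protocol treatment held; cytarabine and anthracyclines barred | High dose cytarabine |
| Duration of the stop | Bar lasts while on trial | Rest of the induction cycle |
| Restart condition | EF at least 45% | None stated |

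**3. Reading the second sentence.** Taken literally, it governs induction, where no high dose cytarabine is given, so it never acts. Taken to mean the cycle under way, it applies post-remission and stops less, for a shorter time, than the first rule. In both cases, following the first rule satisfies the second.

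**4. The restart test.** LVEF of at least 45% is already an entry criterion (Section 4.2, criterion 6). A subject with isolated cerebellar toxicity and unchanged EF therefore meets the restart condition on the day of the hold. With cytarabine and anthracyclines barred, the Group A drug left to restart is ENTO.

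**5. Other text that might supply a neurologic criterion.**
- The general rule to hold until less than Grade 2 covers only clinically significant related toxicity of Grade 3 or greater.
- The Group A rule under which a subject "will hold dosing of ENTO until the toxicity resolves to Grade 1, and then restart at the next lower dose" covers only ENTO-related toxicity of Grade 3 or higher.
- The opening of Section 3.3 lets subjects who are intolerant beyond Cycle 1 stop the drug or "have a dose hold in consultation with the Medical Monitor if the AE or lab has resolved to Grade 1 or less". This is one option, not a restart rule for this event.
- Section 5.1.1 tells sites, for the chemotherapy drugs, to "please follow the currently approved version of the package insert and institutional guidelines when administering". That does not govern ENTO.
- Appendix 3 has no cerebellar row. Its row for other drug-related non-hematologic events keeps the dose at Grades 1-2. The end of Section 3.3 assigns the appendix to Group C, although the section's opening also cites it.
- Section 6.4.1 allows discontinuation for toxicity on the investigator's judgment, without a recovery grade.

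None of these sets a neurologic recovery level for a cerebellar hold below Grade 3.

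**6. From when it applies.** In Group A, toxicity in Cycle 1 that requires permanent discontinuation of either drug removes the subject from study. The first rule bars cytarabine for good, so a Cycle 1 event appears to fall under that removal. The restart question therefore arises from induction Cycle 2 onward.

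**The case against.** The strongest reply is that nothing in the two rules obliges a site to breach either one. The second sentence can be read as an immediate within-cycle action and the first as the trial-long bar. That is right, and it limits the point. A reader might infer that the second sentence permits re-treatment that the first forbids. The documents do not support this: the sentence says when to stop and is silent on what follows, and silence is not permission. For the same reason, no number of later cytarabine cycles can be said to be left open, since that would require rewording the second sentence and setting the first aside.

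A reader might also infer that the bar applies from Grade 1 and count grades on that basis. The first rule gives no grade, and the word florid (misspelled in the protocol) may qualify cerebellar toxicity as well as heart failure, which would mean overt toxicity. A Grade 1 trigger is one reading, not a stated rule.

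It can further be said that restart is never automatic. Investigator judgment and the Medical Monitor stand in the way, and neither rule attributes cerebellar toxicity to ENTO. That reduces the risk but does not repair the text. The protocol holds ENTO for this event and then states a restart condition that does not test it.

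**Conclusion.** The point holds as a minor safety-wording correction with two parts. The cerebellar sentence in the hematologic block is misplaced and, as worded, has no effect; it matters only for Group A Phase 2 subjects in post-remission cycles. The EF-only restart condition does not test neurologic recovery, and other text fills the gap only in part; this part applies to Group A from induction Cycle 2 onward.

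The practical reach is small. Group A enrollment is complete (Sections 3.1.1 and 3.1.2), and SAP Section 1 says that the study will be terminated early. The documents do not say how many subjects could still receive cytarabine or ENTO. No endpoint, analysis set or estimate changes.

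The conclusion assumes that high dose cytarabine means the gram-dose post-remission regimens, that the cerebellar event leaves EF at 45% or more, and that ENTO is what would resume. It does not depend on the grade at which the first rule is triggered, so it does not support a separate restart provision for Grade 1.

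**What to change.** Three wording changes in Section 3.3, Group A:

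1. Delete the cerebellar sentence from the hematologic block. Alternatively, move it to the non-hematologic block and reword it for post-remission cycles so that it matches the first rule's permanent bar.
2. Limit the restart condition of EF at least 45% to the heart-failure case.
3. State that, after cerebellar toxicity, held ENTO may resume only once the toxicity has resolved to less than Grade 2. That is the level in the general rule of the same block, and it agrees with the Grade 1 level in the Group A ENTO rule.

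Until the text is changed, sites should follow the stricter rule in the non-hematologic block. A clarification letter or amendment wording is enough; no procedures or subjects are added.
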